7.2.2 Summary of Recent Safety and Efficacy Data

Appis et al. recently reviewed articles reporting safety and efficacy data.(71) Table 5 summarizes the key findings from these articles.

Table 5: Summary of Perflutren Lipid Microsphere Safety Data

Citation	Population studied	Analysis Design	Key Safety Findings
(74)	1,513 inpatients with pulmonary hypertension	Retrospective series	3/1513 patients had any SAE and none were directly attributed to perflutren itself
(75)	63,189 patients undergoing 96,705 transthoracic echocardiograms, including 2,518 using perflutren	Retrospective series	24-hour mortality was 0.44% in the definity group and 0.69% in the non-contrast group ($p=0.14$). Use of perflutren was not associated with increased mortality in multivariate analysis.

(76)	5,576 patients undergoing contrast-enhanced echocardiograms	5,956	Retrospective series	16 adverse events occurred (0.27%), all mild and transient, most commonly back pain and rash. No SAEs occurred.
(77)	39,020 perflutren-enhanced echocardiograms including in 418 patients with known right to left intracardiac shunts		Retrospective series	No neurological or systemic embolism events occurred. Most common secondary adverse event was back pain (25/39,020)

Package labelling reports adverse reactions from a total of 1,716 subjects studied in pre-market clinical trials.(70) Of these, 144 (8.4%) had at least one adverse reaction. Table 6 summarizes the adverse reactions occurring in at least 0.5% of participants.

Table 6: Summary of Adverse Reactions from Perflutren Lipid Microsphere Package Insert

Adverse Reaction	Number of events (%)
Injection site reaction	11 (0.6%)
Back/renal pain	20 (1.2%)
Chest pain	13 (0.8%)
Pain in body as a whole	41 (2.4%)
Headache	40 (2.3%)
Dizziness	11 (0.6%)
Nausea	17 (1.0%)
Flushing	19 (1.1%)

Extrapolating these safety data—collected from patients with known cardiac disease—to the relatively younger, otherwise-healthy T1DM and control populations of this study suggests the risk of a serious or non-serious adverse event from perflutren infusion is low. Nonetheless, we will take important safety precautions in this elective research study.

7.2.3 Safety Provisions to Mitigate Adverse Events Associated with Perflutren Lipid Microspheres

Because perflutren is not FDA approved for use in the pediatric population, we will only use CEUS in adult participants.

The informed consent document will include the previously mentioned risks associated with perflutren lipid microsphere infusion and discussed during the consent process. The PI will be physically present throughout the

STUDY visits, which include two infusions of perflutren lipid microspheres. Further, the PI will be under the supervision of a board-certified cardiologist ([name]) and internist ([name]) who have extensive experience using this technique. The PI will discuss the conduct of the study on a routine basis. In rare circumstances, the PI may elect to allow a designed KSP (MD, NP, or PA) to provide medical supervision in his absence. STUDY visits will be conducted in the Vanderbilt Clinical Research Center, a state-of-the-art facility that has cardiac monitoring and resuscitation equipment readily available. Vital signs will be monitored throughout each STUDY visit.

7.3 Anemia

For STUDY B-C we will collect a small blood sample (10 mL) at the screening visit. This blood sample will include a complete blood count (CBC) test to ensure each participant's hematocrit is at least 35%.

Within eight weeks of the screening visit, we will conduct two hyperglycemic, euglycemic clamps on STUDY B-C (Aim 3) participants, with up to one month separating each study (see section 6.2). The total amount of blood drawn in each STUDY B-C visit equals 127 mL. This includes the volume of fluid in the angiocatheter that must be cleared with each blood draw to ensure blood samples are not diluted (41 mL in total). This fluid, often called "waste," is mostly saline running through the angiocatheter to ensure the catheter remains patent but contains some blood. Thus, the maximum amount of total blood drawn in each study is calculated to equal 127 mL. Thus, we calculate a maximum volume from the STUDY B-C visits of 254 mL over one month.

As reviewed in a World Health Organization Bulletin,(78) while several guidelines are available for reference, there is a limited amount of direct evidence on which to base them. We have set 50 kg as the minimum required body mass STUDY B-C participants to align with guidance from the Wayne State University Institutional Review Board for Minimal Risk blood collection which states:

"When the collection of blood samples presents minimal risk to adult subjects they may be one by finger stick, heel stick, ear stick, or venipuncture under the following conditions and guidelines:

- a. Blood samples may be collected for research purposes from healthy, nonpregnant adults who weigh at least 110 pounds. The amounts drawn may not exceed 550 ml in an 8 week period and collection may not occur more frequently than 2 times per week".(79)

Further, our approach aligns NIH policy M95-9(rev.) "Guidelines for Limits of Blood Drawn for Research Purposes in the Clinical Center." For adult patients and volunteers, the policy states, "The amount of blood that may be drawn from adult

patients and volunteers (i.e., those persons 18 years of age or older) for research purposes shall not exceed 10.5 mL/kg or 550 mL, whichever is smaller, over any eight week period."

STUDY 1-5 poses less risk for anemia. The total blood volume drawn in each STUDY 1-5 visit is 124 mL. Although longitudinal study (STUDY 1-3) participants are studied three times, each study visit is separated by more time. We do not anticipate the time between STUDY1 and STUDY2 will ever be less than 1 month and anticipate the normal interval between STUDY1 and STUDY2 will be between 2-4 months.

In addition to obtaining a complete blood count at screening, the PI will clinically monitor all volunteers for signs and symptoms of anemia throughout their participation. Specifically, the PI will monitor participants for easy fatigability, lassitude, muscle cramps, postural dizziness, or recent onset of dyspnea. If these clinical signs and symptoms are present, a repeat hematocrit will be ordered. If hematocrit is < 35%, the participant will be excluded from further study.

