6.0 Study Procedures

6.1 Research visits: STUDY1-7 (Aims 1-2)

All subjects will participate in a screening visit ([section 6.1.1](#)) then will participate in one of two substudies based on whether they are a participant recently diagnosed with T1DM (T1DM SUBSTUDY) or if they are a healthy control participant without T1DM (CONTROL SUBSTUDY). Figure 5 summaries the T1DM and CONTROL substudies.

[figure not shown]

Figure 5: Schematic for STUDY visits. Est. = estimated.

PCR=partial clinical remission. $TDD_{insulin}$ = total daily dose of insulin

1. Participants selected for the **T1DM SUBSTUDY (n=20)** will have a T1DM duration of less than one year. They will participate in three identical STUDY visits (STUDY1-3).
 - STUDY1 will occur within 1-3 months of diagnosis in most instances. In our practice, the initial starting total daily dose of insulin ($TDD_{insulin}$) upon diagnosis is usually 0.5 units/kg/day.(56) STUDY1 will require each participant's $TDD_{insulin}$ averaged over 5 consecutive days fall between 0.4-

0.6 units/kg/day, which is a common dosing range during the first 2-3 months after diagnosis.

- For participants to enter STUDY2, their mean TDD_{insulin} must be \leq 0.4 units/kg/day. This usually occurs between 3-6 months post-diagnosis.
- To enter STUDY3, the TDD_{insulin} must exceed or equal 0.6 units/kg/day, which usually occurs by 12 months post-diagnosis.

2. Participants selected for the CONTROL SUBSTUDY (n=20) will not have T1DM and have no chronic illnesses. They will participate in STUDY 4-7 (each CRC study visit follows the same protocol).

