6.1.1.6 Basal insulin instructions for CONTROL SUBSTUDY participants

CONTROL SUBSTUDY participants (who do not have diabetes) will inject low doses of subcutaneous insulin glargine (0.2 u/kg/day) over 7 days preceding STUDY 6 and 7 and placebo over 7 days preceding STUDY 4 and 5. The study team will show these participants how to properly perform these injections at home. Please see section 7 regarding risk mitigation measures to prevent serious hypoglycemia.

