6.1.3.10 CLAMP sampling period (SAMPLE)

A second sampling period will measure the blood parameters listed in table 3 under insulin-stimulated conditions during the last 30 minutes of the clamp.

The total blood volume from each study is calculated to equal 124 mL.

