6.1.3.13 Rescheduling STUDY visit after a technical issue

It is possible once a clamp visit has begun a technical issue will prevent the successful completion of the study. For example, IV access may be lost during the study or otherwise uneventful hypoglycemia (glucose < 55 mg/dL) may occur for those participants receiving an overnight IV insulin infusion. In the event such a technical issue occurs, the PI may elect to reschedule a new, repeat STUDY visit provided he deems the technical issue poses no serious danger to the participant were it to occur again and the participant wishes to repeat the study.

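### Section 7.3's lower-anemia-risk statement gives no support for the four-visit control substudy, whose planned 496 mL per person is never totalled or checked against the 8-week limit the section cites

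*Combined protocol and SAP*

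**What the plan says.** Section 7.3 works through blood volume for STUDY B-C. It gives 127 mL per visit, 254 mL over two visits and a 10 mL screening sample. It sets a 50 kg minimum body mass and says the approach aligns with an NIH policy under which research blood "shall not exceed 10.5 mL/kg or 550 mL, whichever is smaller, over any eight week period". That policy covers adults ("those persons 18 years of age or older").

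The section then turns to Aims 1-2: "STUDY 1-5 poses less risk for anemia. The total blood volume drawn in each STUDY 1-5 visit is 124 mL". The reason follows: "Although longitudinal study (STUDY 1-3) participants are studied three times, each study visit is separated by more time". It adds that STUDY1 and STUDY2 are not expected to be less than a month apart and will usually be 2 to 4 months apart. No reason is given for controls.

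Elsewhere in the protocol:

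- Section 6.1, on control participants: "They will participate in STUDY 4-7 (each CRC study visit follows the same protocol".
- Section 6.1.3.10, on Aims 1-2 visits: "The total blood volume from each study is calculated to equal 124 mL".
- Section 6.1.1.6 has controls inject glargine "over 7 days preceding STUDY 6 and 7 and placebo over 7 days preceding STUDY 4 and 5". This is the only spacing that the readable text implies for them.
- Table 1 sets a BMI of 18-28 kg/m² for STUDY 1-7 and no minimum body mass.
- Section 6.1.3.13, after a technical failure: "the PI may elect to reschedule a new, repeat STUDY visit provided he deems the technical issue poses no serious danger". The participant must also agree. Blood already drawn is not a condition.

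**The concern.** The lower-risk statement rests on an argument that cannot apply to controls. STUDY 1-3 visits are spread over roughly a year, whereas the control visits have no stated interval and could follow one another closely. Controls also have the largest planned blood volume in the protocol, and they are healthy volunteers.

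The standard is applied unevenly. The 50 kg floor follows guidance written for healthy adults of at least 110 pounds. Controls are healthy adults, yet the floor applies to STUDY B-C only. An IRB member reading 7.3 would conclude that controls are the lower-volume group and would find no total to correct that impression. At stake are an accurate risk description and a check that keeps a light control, or one who repeats a visit, within the limit that the protocol itself cites.

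**Working it through.** **Inputs.** 124 mL per STUDY 1-7 visit (6.1.3.10, 7.3); four control visits (6.1); 127 mL per STUDY B-C visit, 10 mL screening and 41 mL waste per B-C visit (7.3); limit min(10.5 mL/kg, 550 mL) per 8 weeks (7.3); BMI floor 18 (Table 1).

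**Step 1: the plan's own figure.** STUDY B-C: 2 × 127 = 254 mL, as stated; with screening, 264 mL.

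**Step 2: the same arithmetic for Aims 1-2.**

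- STUDY 1-3: 3 × 124 = 372 mL.
- STUDY 4-7: 4 × 124 = 496 mL.
- Controls to STUDY B-C: 496/254 = 1.95. With screening added to B-C only, 496/264 = 1.88.
- If 41 mL of each control visit is also waste (an assumption) and waste is left out of both: 4 × 83 = 332 and 2 × 86 = 172, so 332/172 = 1.93. Waste does not explain the difference.

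**Step 3: control volume in any 56 days, equal gaps assumed.**

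| Gap between visits | Visits in 56 days | Volume |
|---|---|---|
| 7-18 days (3 × 18 = 54) | 4 | 496 mL |
| 19-28 days (3 × 19 = 57; 2 × 28 = 56) | 3 | 372 mL |
| over 28 days | 2 | 248 mL |

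Controls fall below STUDY B-C's 254 mL only with gaps over 28 days.

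**Step 4: four visits against the cited limit.** 496 is below 550. For the per-kg limit, 496/10.5 = 47.2 kg. At BMI 18 that is a height of √(47.24/18) = 1.62 m. Someone of 1.60 m at BMI 18 weighs 18 × 1.60² = 46.1 kg and has a limit of 484 mL, 12 mL below the planned volume. The STUDY 1-7 screening volume is not stated. If it is 10 mL and falls in the same 8 weeks, the threshold is 506/10.5 = 48.2 kg.

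**Step 5: one repeat, with all five draws within 8 weeks (equal gaps of 14 days or less, since 4 × 14 = 56).** A failed visit drawing 25%, 50% or 100% of 124 mL gives 496 + 31 = 527, 496 + 62 = 558 or 496 + 124 = 620 mL. The 550 mL limit is passed once the failed visit draws more than 550 − 496 = 54 mL (54/124 = 44%). Below 550/10.5 = 52.4 kg the per-kg limit binds first and less is enough: at 50 kg, 525 − 496 = 29 mL.

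**Step 6: sensitivity to waste.** If 41 of each 124 mL is waste and is excluded, four visits are 332 mL (332/10.5 = 31.6 kg) and five full visits are 5 × 83 = 415 mL. Section 7.3 says waste is mostly saline with some blood, so the true figure lies between. Five full visits pass 550 mL only if more than (550 − 415)/(5 × 41) = 66% of the waste is counted.

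**The case against.** The strongest reply is that nothing is breached as planned. The planned volume is under 550 mL, and the per-kg limit is passed only for a light control with all four visits inside 8 weeks and every millilitre counted as blood. That is correct. With waste excluded, the breach scenarios largely disappear.

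Spacing may also be wider than the text shows. Figures 2 and 5 are the visit schematics and are not available here. Controls using a CGM wear it for 7-10 days before each visit (6.1.1.4), and the team contacts participants about 10-14 days before each visit (6.1.2). These make 7-day spacing less likely. They are not minimum intervals, however, and four visits 14 days apart still fit in 8 weeks.

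The repeat case is also narrow. Overnight hypoglycemia, one of the examples in 6.1.3.13, precedes the main sampling, and a visit that drew its full volume is essentially complete. The 620 mL figure is an upper bound, not an expectation.

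Real safeguards cover controls: the hematocrit exclusion in Table 1, a screening blood count (or one from the previous 6 months), symptom monitoring with repeat hematocrit and exclusion below 35%, and withdrawal for risk of harm (section 9.0). They reduce the consequence but do not count volume, and the repeat hematocrit depends on symptoms.

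Finally, the STUDY 1-5 label does include two control visits and recurs in 6.2.1.5, 6.2.3.2, 6.2.3.4 and 10.2.2, so it probably reflects numbering that was not updated. That explains the label, but the missing total and the missing argument for controls remain.

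**Conclusion.** The point holds as a gap in the safety justification, with a modest practical consequence. The lower-risk statement is supported for STUDY 1-3 only. Controls have 496 mL planned, 1.95 times STUDY B-C, and on equal spacing their 8-week volume drops below STUDY B-C's only when gaps exceed 28 days. As written, the readable text allows an eligible control under 47.2 kg, or one with a substantially drawn and then repeated visit, to exceed the limit that 7.3 cites. Both outcomes assume visits close enough to fall within 8 weeks and waste counted as in the protocol's totals.

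A reader might infer three stronger things that the documents do not support:

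- **That the planned control schedule breaches 550 mL.** It does not.
- **That the protocol adopted the limit as a cap for controls and then broke it.** Section 7.3 cites the limit while discussing STUDY B-C only. It is a suitable yardstick because it covers adults and section 7.5 restricts controls to adults.
- **That STUDY B-C has the same problem.** Repeating both visits in full, with screening, gives 4 × 127 + 10 = 518 mL, against 10.5 × 50 = 525 mL at the mass floor.

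This is a low-cost improvement and does not call the design into question.

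**What to change.** In 7.3, limit the lower-risk sentence to STUDY 1-3 and state the planned 4 × 124 = 496 mL for STUDY 4-7. Add this rule, with a reference to it from 6.1.3.13:

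*A STUDY 4-7 visit, including any repeat, is scheduled only if the participant's total research blood over any 8 weeks (screening and failed visits included) stays within the smaller of 10.5 mL/kg or 550 mL; otherwise it is deferred.*

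No change is needed for STUDY B-C. Participants under 18 fall outside the cited adult limit and outside this point.

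The cost is one corrected sentence, one added total, one scheduling rule and one cross-reference. In practice a control visit or repeat will occasionally be deferred. A control under 47.2 kg would need gaps of at least 19 days if they are equal, which puts three visits (372 mL) in any 8 weeks. The rule defers visits and does not exclude light controls, so eligibility is unchanged.

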7.4 Hypotension

Nitroglycerin is administered sublingually during the flow mediated dilation studies. This may cause a fall in blood pressure and symptoms of hypotension. To avoid the latter, nitroglycerin will not be administered to any participant whose systolic blood pressure is \leq 100 mmHg.

7.5 Special Protections for Adolescents as Research Subjects

Because the study includes adolescent T1DM subjects between ages 15-18, special consideration has been given to provisions designed to protect children as outlined in 45 CFR 46, Subpart D. Because adolescent participants without T1DM would not meet the criteria of 45 CFR 46.406, control participants will only include adult participants.

7.5.1 Justification and rationale for inclusion of adolescent subjects with T1DM

The atherosclerotic changes of macrovascular disease in T1DM (e.g. increasing carotid intima media thickness) appear to begin in childhood and adolescence(80, 81) and morbidity and mortality risk is staggeringly high in younger adults.(10) As an example, among individuals ages 1-39, the standardized mortality risk (i.e. ratio between the observed number of deaths in a study population and the number of deaths that would be expected) for ischemic heart disease death is 8.9 (95% CI 6.2–12.9) in males and an astounding 41.7 (95% CI 28.9–58.2) in females. Thus, it is clear that pathophysiologic mechanisms that contribute to macrovascular

disease are operative *early in the natural history of T1DM*. These same early pathophysiologic mechanisms have not been identified, however.

To date *only one study* has examined pediatric T1DM patients with typical glycemic control, which found that adolescents were 37% less insulin sensitive than matched control subjects,(9) *suggesting that exposure to insulin resistance begins early in the natural history of T1DM*.

To determine the root cause of T1DM insulin resistance and translate this information into therapies that would ameliorate insulin resistance in T1DM and its contribution to macrovascular disease, the endocrine and molecular mechanisms causing insulin resistance must be assessed early in the disease duration. This is because:

- 1) T1DM insulin resistance appears to begin early in the disease process.(9, 28)
- 2) The incidence of T1DM onset is highest between ages 10-14.(82)
- 3) At younger ages and shorter disease durations there are minimal confounding covariables that would contribute to insulin resistance at a molecular level. These confounding covariables include co-morbidities associated with T1DM such as diabetic nephropathy,(83) prolonged exposure to hypertriglyceridemia,(84, 85) excessive BMI(86, 87) and visceral adiposity,(88, 89), deleterious effects of aging and progressive inflammation on extracellular matrix remodeling,(90, 91) and increasing age per se.(92, 93)

By studying adolescent and young adults early in the disease duration, this investigation will more precisely determine iatrogenic hyperinsulinemia's association with insulin resistance and endothelial dysfunction at a very early point in the course of T1DM when confounding covariables are minimal. This knowledge is critical towards guiding subsequent therapy to mitigate insulin resistance and endothelial dysfunction, which will considerably reduce early mortality risk from macrovascular disease in the same subjects tested in the research.

7.5.2 [Assessment of risk to adolescent participants relative to 45 CFR part 46, subpart D](#)

It is our impression that T1DM subjects would fall under 45 CFR 46.406, as outlined in Vanderbilt's Human Research Protections Program Policy Number IX.A, section II.C. The proposed research is likely to yield generalizable knowledge about these adolescents' condition. Specifically,

1. The risk represents a minor increase over minimal risk.

- The hyperinsulinemic, euglycemic clamp has been used safely in adolescents by the PI and elsewhere. The technique has been performed over one thousand times in healthy adolescent subjects at other institutions such as the University of Minnesota,(94-97) hundreds of times in overweight adolescent(98-100) and normal weight prepubertal subjects(101, 102) at the University of Pittsburgh, and a similar number of times in normal weight children and adolescents at the National Institutes of Health.(103, 104) Our insulin maximal infusion rate of 40 mU/m²/min is approximately equal to the rate used in studies of healthy subjects at each of these institutions and half that used in overweight subjects studied at the University of Pittsburgh.
- As outlined in section 7.1, extensive efforts have been employed to minimize risk of hypoglycemia and hypokalemia associated with hyperinsulinemia.
- The PI has personally performed the hyperinsulinemic, euglycemic clamp over 80 times in human subjects and nearly as many times in canine studies.

2. The procedure presents experiences to participants that are reasonably commensurate with those inherent in their actual or expected medical situation.
 - Hypoglycemia is a fact of life for most patients with insulin-treated diabetes. The average patient with T1DM experiences two episodes of hypoglycemia per week.(95) Every effort will be made to prevent hypoglycemia from occurring during the clamp study at all, however.
3. The procedure is likely to yield generalizable knowledge about the participants' disorder or condition, which is of vital importance for the understanding or amelioration of the participants' disorder or condition.
4. Adequate provisions are made for soliciting assent of the children and permission of their parents or legal guardians as detailed in the present IRB application.

